7.4.3.2. Vital Signs

Changes from Baseline in vital signs (blood pressure, heart rate, respiratory rate, and body temperature) at each visit will be summarized descriptively by group and overall. Missing vital signs data will not be imputed and only scheduled assessments will be summarized in tables; unscheduled assessments will be presented in data listings. A listing of vital signs will be presented by participant, vital sign, and visit.

7.4.3.3. Physical Examination

Abnormal physical examination results will be tabulated by study visit and body system. Physical examination data (including height and weight) will also be listed by scheduled visit.

7.4.3.4. Electrocardiogram

All ECG data will be fully listed and changes from Baseline in ECG data (heart rate, PR interval, RR interval, QRS duration, QT interval) will also be summarized descriptively by scheduled visit.

All QT intervals will be corrected for heart rate according to Fridericia ($QTcF = QT/(RR^{1/3})$). At each time point, the number and percentage of participants falling into the following categories according to the International Conference on Harmonization (ICH) E14 Guidelines will be presented:

- QTc actual values: ≤ 450 ms, >450 to ≤ 480 ms, >480 to ≤ 500 ms, and >500 ms
- QTc increases from Baseline of >30 msec and >60 msec

Changes from Baseline in QTc will also be summarized. Further, ECG data will be classified by the Investigator as “normal,” “abnormal, not clinically significant,” “abnormal, clinically significant” or “indeterminate” at each timepoint assessed. Summary results will include the count and percentage of participants within each category at each visit.

7.5. Pharmacokinetic and Pharmacodynamic Analyses

For PK and PD endpoints, analyses will be performed using the PK/PD Analysis Set.

7.5.1. Pharmacokinetic Concentration Analyses

Plasma concentrations of total Mo and PUF Mo (as surrogate measures of ALXN1840 PK) and time data will be presented in a data listing by participant. Plasma concentration data will be summarized separately by analyte, day and time point using the following descriptive statistics: number of participants, arithmetic mean, SD, coefficient of variation (CV), geometric mean

(GM), GMCV, median, minimum, and maximum. When calculating the GM, values of 0 will be discarded. For summary statistic calculations, plasma concentrations values below the lower limit of quantification (LLOQ) will be set to the LLOQ.

Mean plasma concentration versus scheduled time profiles will be presented in figures on both linear and semilogarithmic scales. Individual plasma concentration versus actual time profiles will be presented similarly. The time to reach steady-state will be graphically assessed by plotting mean plasma trough (predose) concentration observed at the start of the dosing interval (C_{trough}) versus study day in both linear and semilogarithmic scales. Additionally, time to steady state will be evaluated using stepwise testing for linear trend.

7.5.2. Pharmacodynamic Concentration Analyses

Individual ALXN1840 PD and biomarkers, assessed as plasma total Cu (PD), toxic Cu measured as plasma PUF Cu (PD), LBC (PD), NCC/non-ceruloplasmin-bound Cu concentration corrected for the amount of Cu bound to the Cu-tetrathiomolybdate-albumin tripartite complex formed after ALXN1840 administration ($NCC_{\text{corrected}}$) (PD), and Cp (biomarker) and CpC (biomarker) concentration-time data (including measured, absolute change from Baseline and percent change from Baseline) will be listed by participant.

The PD and biomarker concentration (measured, absolute change from Baseline and percent change from Baseline) data will be summarized separately by analyte, day and time point using the following descriptive statistics: number of participants, arithmetic mean, SD, CV, GM, GMCV, median, minimum, and maximum. When calculating the GM, values of 0 will be discarded. For PD and biomarker summary statistic calculations, concentrations below the LLOQ will be set to the LLOQ.

Mean PD and biomarker concentration (measured, absolute change from Baseline and percent change from Baseline) versus scheduled time profiles will be presented in figures on linear scales. Individual PD and biomarker concentration (measured, absolute change from Baseline and percent change from Baseline) versus actual time profiles will be presented similarly.

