## 4.2. Scientific Rationale for Study Design

As both healthy and WD animal models have supported the characterization of tetrathiomolybdate's (ALXN1840) mechanism of action, namely liver Cu depletion through mobilization of Cu into plasma and bile and excretion into feces, healthy participants are adequate for assessing the mechanism of action of ALXN1840 on Cu balance, which is the primary objective of this study. The inclusion and exclusion criteria for this study are consistent with typical Phase 1 clinical pharmacology studies for assessing the medication of interest. To limit the risk of Cu depletion in healthy participants (or the risk of recruiting participants with abnormal Cu metabolism), only participants with serum Cu and ceruloplasmin above the lower limit of normal will be included.

The 15-day duration for ALXN1840 dosing is supported by both preclinical and clinical data. Preclinical models suggest that Cu excretion in feces may be increased or at least sustained with repeated-dose administration over 5-8 days. With gastrointestinal transit in humans being somewhat longer than most animal models (Mason, 1988; Ogra, 2000), a 15-day repeat dose is considered reasonable. Based on studies in oncology patients, a dose of 30 mg/day for 28 days resulted in a substantive reduction in ceruloplasmin (Lin, 2013). Copper-containing ceruloplasmin, known as holo-ceruloplasmin, has a half-life of approximately 5 days, and serum ceruloplasmin concentrations (largely determined by holo-ceruloplasmin) are indicative of reduction in total body Cu load (Harris, 1997; Sternlieb, 1961). Taken together, a dose of 30 mg/day for 15 days is expected to result in a net negative Cu balance in healthy participants with an acceptable safety profile.

Following ALXN1840 administration, the active drug moiety tetrathiomolybdate rapidly binds Cu to form TPC in the liver and blood and presents as such in the systemic circulation. If TPC is not rapidly formed, tetrathiomolybdate spontaneously undergoes serial hydrolysis to form molybdate, the most common form of nutrient Mo, and is excreted in the urine. Total Mo concentration has been measured as a surrogate of ALXN1840 PK; however, total Mo

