### 9.4. Statistical Analyses

Statistical methods described in this section will be further elaborated in a separate Statistical Analysis Plan (SAP). Summary statistics will be computed and displayed by day and period (predose baseline, treatment, steady state, and post-treatment) where applicable. Descriptive statistics for continuous variables will minimally include the number of participants, mean, SD, minimum, median, and maximum. For categorical variables, frequencies, and percentages will be presented. Graphical displays will be provided as appropriate.

Analyses will be performed using the SAS® software Version 9.4 or higher.

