### **9.4.3. PK/PD Analyses**

For PK endpoints, analyses will be performed using the PK Analysis Set. Individual plasma total Mo and PUF Mo (as surrogate measures of ALXN1840) concentration-time data will be listed and plotted. The following total Mo (ALXN1840) PK parameters will be derived for individual participants and summarized with descriptive statistics. Analyses of PUF Mo may also be conducted:

- Maximum observed concentration ( $C_{max}$ ), time to maximum concentration ( $t_{max}$ ), AUC from time 0 to the time of last measurable concentration ( $AUC_t$ ), AUC from time 0 to infinity ( $AUC_{\infty}$ ), apparent terminal-phase elimination rate constant ( $\lambda_z$ ),  $t_{1/2}$ , clearance bioavailability (CL/F), and apparent volume of distribution ( $V_d/F$ ).

For exploratory endpoints such as plasma total Cu, ceruloplasmin, ceruloplasmin-bound Cu, and toxic copper as measured by LBC and/or NCC, a concentration-time data will be listed and summarized with descriptive statistics and plotted. The same analyses will be conducted on the absolute and percent changes from baseline of these concentration-time data.

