9.2.6. Change From Baseline

Change from Baseline will be calculated as: post-Baseline assessment value – Baseline assessment value when both values are not missing.

Percent change from Baseline is calculated as $(\text{change from Baseline} / \text{Baseline result} * 100)$.

If either the Baseline or the post-Baseline result is missing, the change from Baseline and/or percentage change from Baseline is set to missing. Additionally, if the Baseline is 0, the percentage change from Baseline will be missing.

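### SAP 7.5.2 plans geometric means and geometric CVs for changes from baseline, which can be negative, so these cells are undefined or describe only participants whose value rose

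*SAP*

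**What the plan says.** SAP 7.5.2 covers plasma total Cu, PUF Cu, LBC, NCC/NCCcorrected, ceruloplasmin and ceruloplasmin-bound Cu. It groups three kinds of data together: "The PD and biomarker concentration (measured, absolute change from Baseline and percent change from Baseline) data will be summarized separately by analyte", by day and time point, "using the following descriptive statistics: number of participants, arithmetic mean, SD, CV, GM, GMCV, median, minimum, and maximum". Nothing limits GM, GMCV or CV to the measured values.

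Two handling rules follow. One concerns the GM: "When calculating the GM, values of 0 will be discarded". The other sets concentrations below the LLOQ to the LLOQ. Neither mentions negative values, and SAP 9.3, the place for further statistical detail, is marked not applicable.

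SAP 9.2.6 defines change from baseline as "post-Baseline assessment value – Baseline assessment value when both values are not missing". For the relative version, "Percent change from Baseline is calculated as" that change divided by the baseline result, times 100.

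The protocol does not ask for geometric statistics. Section 9.4 says: "Descriptive statistics for continuous variables will minimally include the number of participants, mean, SD, minimum, median, and maximum". Section 9.4.3 extends the descriptive summaries to changes: "The same analyses will be conducted on the absolute and percent changes from baseline of these concentration-time data". GM and GMCV enter only in the SAP.

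**The concern.** The logarithm of a negative number is undefined, so GM and GMCV cannot be computed for a set of changes that contains any fall. The SAP leaves the programmer to choose between a missing cell and a cell computed after negatives are dropped. The second choice selects participants by the sign of the outcome being summarized.

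For at least one analyte the protocol points to a fall. Section 4.2 says of earlier oncology experience that "a dose of 30 mg/day for 28 days resulted in a substantive reduction in ceruloplasmin". If ceruloplasmin falls in most participants here, a GM over the remaining positive values would be a positive number in a table of a falling biomarker. Absolute and percent changes in ceruloplasmin, ceruloplasmin-bound Cu, their ratio and LBC form a named exploratory endpoint (SAP 5.2.3), so such tables will be read.

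The arithmetic CV has a related weakness. It divides by the mean change, which may be close to zero or negative.

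**Working it through.** The documents state no figure on this point, so there is none to reproduce. The check is of definitions, followed by illustrations under stated assumptions.

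**1. Definitions.** GM = exp(mean of ln x). GMCV = 100 × √(exp(variance of ln x) − 1). Both need every x > 0. Change = post − baseline (SAP 9.2.6), and percent change has the same sign because concentrations are positive.

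**2. Do the other rules help?**
- Discarding zeros leaves negatives in place.
- Setting values below the LLOQ to the LLOQ acts on concentrations and does not make a change positive. It also means a directly assayed concentration cannot be zero, so for those analytes the zero rule acts mainly on changes. A participant below the LLOQ at both baseline and follow-up has a change of exactly 0 and leaves the GM.

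**3. Share of negative values.** Assume percent change is normal with mean m and SD s. The share below zero is Φ(−m/s).

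| Mean change | SD 10% | SD 15% | SD 20% |
|---|---|---|---|
| −5% | 69% | 63% | 60% |
| −10% | 84% | 75% | 69% |
| −20% | 98% | 91% | 84% |
| −30% | 99.9% | 98% | 93% |

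For example, at −10% with SD 15%: Φ(10/15) = Φ(0.667) = 0.748.

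**4. Chance that the GM is defined for everyone.** With the 13 evaluable participants of SAP 9.1, this is p^13, where p is the chance of a positive change.
- Mean −10% to −30%, SD 10% or 20%: below 0.0001.
- Mean 0: 0.5^13 = 0.0001.
- Mean +10%: 0.841^13 = 0.11 (SD 10%) or 0.691^13 = 0.008 (SD 20%).
- Mean +20%: 0.74 (SD 10%) or 0.11 (SD 20%).

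The problem is therefore not confined to falling analytes. It appears wherever some participants fall.

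**5. If non-positive values are dropped.** The expected number left is 13p.
- Mean −20%, SD 10%: 0.3 participants; the chance of fewer than 2, hence no GMCV, is 0.97.
- Mean −20%, SD 20%: 2.1 participants; 0.37.
- Mean −10%, SD 20%: 4.0 participants; 0.06.

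In simulation with SD 10% or 20% and means of −10% to −30%, the GM of the remaining values averaged about +3% to +10%, although the true mean was negative.

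**6. An invented example.** Thirteen percent changes: −35, −30, −28, −25, −22, −20, −18, −15, −12, −8, −5, +4, +9.
- Arithmetic: mean −205/13 = −15.8%, SD 13.1, median −18%.
- GM after dropping non-positive values: √(4 × 9) = +6.0%, GMCV 62%, from 2 of 13 participants.
- Ratio to baseline (1 + change/100, positive whenever the follow-up concentration is): geometric mean 0.833, that is −16.7%, GMCV 15.4%, from all 13.

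**7. Arithmetic CV.** In the same example, CV = 13.1/(−15.8) = −83%, and a negative CV has no useful reading. With SD 15%, moving the mean change from −1% to +1% moves the CV from −1500% to +1500%.

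**The case against.** The strongest reply is that valid summaries of change are already planned. The same sentence of SAP 7.5.2 provides n, mean, SD, median, minimum and maximum. Individual changes are listed and plotted, and mean changes are plotted on linear scales. SAP 7.3.3 analyzes the exploratory endpoints as the primary endpoint is analyzed, which under 7.3.1 means descriptive statistics with 95% confidence limits for the mean change. All of this stands. The fault is bad cells beside good ones.

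Three stronger readings are tempting, and the documents do not support them:

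- **That the SAP will report an effect in the wrong direction.** It tells the programmer to discard zeros, not negatives. A missing cell is equally possible and misleads nobody. The wrong-sign result is a risk left open, not an instruction.
- **That most changes will be negative for every analyte.** The documents support a fall in ceruloplasmin, which protocol 4.3 calls only moderate at 30 mg/day, and in NCCcorrected in patients with Wilson disease. They state no expected direction for LBC, total Cu or PUF Cu in healthy participants. Protocol 4.2 describes mobilization of copper into plasma, so a fall in total Cu cannot be assumed. Sampling also starts 1 hour after the first dose, while section 4.2 gives holo-ceruloplasmin a half-life of about 5 days.
- **That zeros are lost from all summaries of change.** The rule applies only to the GM; the arithmetic statistics keep them.

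The SDs used above are assumptions, so the percentages illustrate the mechanism and do not forecast a loss in this study.

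**Conclusion.** The point holds as a specification error of low severity. As written, GM and GMCV are requested for quantities that can be negative, and no rule in the SAP makes them computable. They will be undefined or will rest on a subset chosen by sign. For an analyte that falls, that subset is likely to be a minority: with an assumed SD of 15%, 63% to 98% of values are negative for mean changes of −5% to −30%. For an analyte that rises, the participants who fell would be excluded instead.

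The defect itself rests only on the definitions in SAP 7.5.2 and 9.2.6. Its size rests on an assumed normal distribution and assumed SDs.

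A reader might infer that the study's conclusions are at risk. They are not. The primary copper balance analysis in SAP 7.3.1 uses no geometric statistic, the study tests no hypothesis, and the arithmetic summaries of change remain valid. GM and GMCV for measured concentrations are not in question.

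**What to change.** Amend SAP 7.5.2 as follows:

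1. Restrict GM, GMCV, CV and the zero-discard rule to measured concentrations.
2. For absolute and percent change, report only the n, mean, SD, median, minimum and maximum that are already planned.
3. If a summary on the ratio scale is wanted, report the geometric mean of the post-baseline/baseline ratio.

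The cost is one or two sentences in the SAP and matching edits to the table shells. It needs no new data, and no protocol amendment, because protocol 9.4 and 9.4.3 do not call for geometric statistics.

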7.5.3. Pharmacokinetic Parameter Analyses

The following plasma PK parameters, as data permit, will be calculated for total Mo and PUF Mo on Day 1 and Day 15 using noncompartmental methods with Phoenix[®] WinNonlin[®] (Certara USA Inc., Princeton, New Jersey) Version 8.0 or higher, or SAS Version 9.4 or higher (SAS Institute Inc., Cary, North Carolina), as applicable. Calculations will be based on the actual sampling times relative to the actual reference ALXN1840 dosing times recorded during the study.

- Time delay between the time of dosing and time of appearance of Mo concentration (T_{lag}) in plasma (Day 1 and Day 15)
- Maximum observed concentration (C_{max}) (Day 1 and Day 15)
- Time to maximum concentration (T_{max}) (Day 1 and Day 15)
- Trough (predose) concentration observed at the start of the dosing interval (C_{trough})
- Time of last quantifiable concentration (T_{last}) (Day 1 and Day 15)

- Observed concentration at the end of the dosing interval (C_{τ} , where $\tau = 24$ h) (Day 1 and Day 15)
- Area under the plasma concentration versus time curve (AUC) from time 0 to the last quantifiable concentration (AUC_t) (Day 1 and Day 15)
- AUC from time 0 to infinity (AUC_{∞}) (Day 1 only)
- AUC over the dosing interval (AUC_{τ}) (Day 1 and Day 15)
- Apparent terminal-phase elimination rate constant (λ_z) (Day 1 and Day 15)
- Terminal elimination half-life ($t_{1/2}$) (Day 1 and Day 15)
- Apparent total body clearance (CL/F) (Day 1 and Day 15)
- Apparent volume of distribution (V_d/F) (Day 1 and Day 15)
- Accumulation ratio (AR) calculated as C_{\max} , C_{trough} , and AUC after repeat dosing on Day 15 divided by those after initial dosing on Day 1:
 - $C_{\max, \text{Day15}}/C_{\max, \text{Day1}}$
 - $C_{\text{trough}, \text{Day15}}/C_{\text{trough}, \text{Day1}}$
 - $AUC_{\tau, \text{Day15}}/AUC_{\tau, \text{Day1}}$

Additional plasma PK parameters may be calculated if deemed appropriate.

For the PK analysis, below the limit of quantification (BLQ) values prior to the first measurable concentration will be set to zero with the rest of all other BLQ values treated as missing

Pharmacokinetic parameters derived from plasma concentrations of total Mo and PUF Mo will be presented in data listings and summarized by analyte and day using the following descriptive statistics: number of participants, arithmetic mean, SD, arithmetic CV, GM, GMCV, median, minimum, and maximum.

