7.5.4. Pharmacodynamic Parameter Analyses

The following plasma PD parameters, as data permit, will be calculated for total Cu, PUF Cu, and LBC on Day 1 and Day 15 using noncompartmental methods with Phoenix[®] WinNonlin[®] (Certara USA Inc., Princeton, New Jersey) Version 8.0 or higher, or SAS Version 9.4 or higher (SAS Institute Inc., Cary, North Carolina), as applicable. Calculations will be based on the actual sampling times relative to the actual reference ALXN1840 dosing times recorded during the study.

- Maximum observed effect after dosing (CE_{\max}) (Day 1 and Day 15)
- Time after dosing at which the maximum effect was observed (TE_{\max}) (Day 1 and Day 15)
- Time after dosing at which the last quantifiable concentration was observed (TE_{last}) (Day 1 and Day 15)
- Trough (predose) effect concentration observed at the start of the dosing interval (C_{trough})

- Area under the effect versus time curve (AUEC) from the start of dose administration to the last observed quantifiable concentration (AUEC_t) (Day 1 and Day 15)

Additional plasma PD parameters may be calculated if deemed appropriate.

For the PD parameter estimation, plasma concentrations below the LLOQ will be set to the LLOQ.

Pharmacodynamic parameters derived from plasma concentrations of total Cu, PUF Cu, and LBC will be presented in data listings and summarized by analyte and day using the following descriptive statistics: number of participants, arithmetic mean, SD, arithmetic CV, GM, GMCV, median, minimum, and maximum.

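### Values below the LLOQ are set to the full LLOQ in the plasma summaries and PD parameters with no count of how many, so at time points that are mostly BLQ, means are inflated and falls in PUF Cu and LBC are capped

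*SAP*

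**What the plan says.** Three sections of the SAP replace a BLQ value with the LLOQ itself.

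- Section 7.5.1, concentration tables for total Mo and PUF Mo: "For summary statistic calculations, plasma concentrations values below the lower limit of quantification (LLOQ) will be set to the LLOQ".
- Section 7.5.2, concentration tables for total Cu, PUF Cu, LBC, NCC/NCCcorrected, Cp and CpC, as measured values and as absolute and percent changes from Baseline: "For PD and biomarker summary statistic calculations, concentrations below the LLOQ will be set to the LLOQ".
- Section 7.5.4, PD parameters for total Cu, PUF Cu and LBC: "For the PD parameter estimation, plasma concentrations below the LLOQ will be set to the LLOQ".

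Section 7.5.3 has a different rule for the noncompartmental PK parameters: BLQ values before the first measurable concentration "will be set to zero with the rest of all other BLQ values treated as missing".

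Sections 7.5.1 and 7.5.2 list the statistics to be shown: n, mean, SD, CV, geometric mean and its CV, median, minimum and maximum. The number BLQ is not among them. No LLOQ is stated, and the protocol has no BLQ rule. Individual concentrations are listed by participant.

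**The concern.** A BLQ value lies somewhere between zero and the LLOQ. Replacing it with the upper end of that range gives an error that always has the same sign. PUF Cu and LBC are among the measures that the SAP uses for toxic copper, so they are expected to move down on treatment. If they fall below the LLOQ, the part of the fall beneath it disappears from the summary, and the participants with the largest falls lose the most. If Baseline is BLQ as well, the change is shown as zero.

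Because the tables carry no BLQ count, a reader could not tell a mean made of measurements from one made mostly of the assay limit. At stake are the description of plasma LBC at steady state (part of a secondary endpoint), the absolute and percent changes in LBC (exploratory), and the PUF Cu and Mo concentration tables.

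**Working it through.** **Inputs.** The substitution rules come from SAP 7.5.1, 7.5.2 and 7.5.4. The documents state no figure to reproduce. The distribution, CV and distance from the LLOQ below are assumptions, with concentrations in units of the LLOQ.

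**Step 1: the cap.** For one participant with a quantifiable Baseline b and an on-drug value below 1, the table shows 1/b - 1, whatever the true value is. With a true on-drug value of 0.25:

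- b = 1.5: true 0.25/1.5 - 1 = -83%; shown 1/1.5 - 1 = -33%.
- b = 2: true -88%; shown -50%.
- b = 10: true -98%; shown -90%.

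The cap matters only when Baseline is close to the LLOQ.

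**Step 2: group means.** Take a lognormal with median m and CV 40%, so s = sqrt(ln(1 + 0.4²)) = 0.385.

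- BLQ fraction: f = Φ(-ln m / s).
- True mean: M = m · exp(s²/2) = 1.077 m.
- Mean with BLQ set to c: M · [1 - Φ(-ln m / s - s)] + f · c, where c = 1 for the SAP rule and c = 0.5 for LLOQ/2.

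Example, median 2 falling to 1: the Baseline mean is 2.154 true and 2.159 under the rule; the on-drug mean is 1.077 true and 1.200 under the rule. The true change is 1.077/2.154 - 1 = -50.0%. The change shown is 1.200/2.159 - 1 = -44.4%, an error of 5.6 points.

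| Median, Baseline to on drug | BLQ on drug | True change | BLQ = LLOQ | BLQ = LLOQ/2 | Error, LLOQ | Error, LLOQ/2 |
|---|---|---|---|---|---|---|
| 2 to 0.4 | 99% | -80.0% | -53.6% | -76.4% | +26.4 | +3.6 |
| 1.5 to 0.5 | 96% | -66.7% | -38.6% | -66.5% | +28.0 | +0.1 |
| 2 to 0.7 | 82% | -65.0% | -51.6% | -70.4% | +13.4 | -5.4 |
| 2 to 1 | 50% | -50.0% | -44.4% | -55.6% | +5.6 | -5.6 |
| 3 to 1.5 | 15% | -50.0% | -49.2% | -51.5% | +0.8 | -1.5 |

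Errors are in percentage points. A positive error means that the fall is understated. At 5 to 2.5 (under 1% BLQ) the error under the SAP rule is below 0.1 point.

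**Step 3: inflation of the level itself under the SAP rule**, for CVs from 30% to 80%:

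| BLQ | Arithmetic mean | Geometric mean |
|---|---|---|
| 10% | +0.8 to +0.9% | +1.4 to +3.4% |
| 25% | +3.0 to +3.7% | +4.5 to +11.1% |
| 50% | +9.4 to +15.0% | +12.4 to +32.4% |
| 75% | +22.7 to +45.3% | +27.4 to +78.5% |

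**Step 4: would LLOQ/2 be better?** Above half BLQ it usually is, but there no single mean is worth reporting. At or below half, the table in step 2 shows equal error at 50% BLQ and a slightly larger error for LLOQ/2 at 15%, with the fall overstated both times. With wider spread LLOQ/2 does better on levels: at CV 80% and 50% BLQ the arithmetic mean is off by -4.6%, against +15.0% for the SAP rule. The choice is a trade-off that depends on a spread the documents do not give.

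**Limit of the check.** Step 2 uses the percent change of means. SAP 9.2.6 computes percent change from each participant's own Baseline, which is then summarised, so errors on that scale will differ. The cap in step 1 applies directly to the participant-level change.

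**The case against.** The strongest reply is that nothing shows that any sample will be BLQ. No LLOQ is given, participants must enter with serum Cu and ceruloplasmin not below the lower limit of normal (protocol 5.2), and PUF Mo includes dietary molybdate (protocol 4.2). If BLQ values are rare, the rule does nothing. In a single-arm study meant to show decoppering, a rule that understates the fall is also the cautious choice, whereas LLOQ/2 can flatter the drug. All of this stands. It limits the size of the point and is a reason not to insist on LLOQ/2. It does not explain why the tables should omit the BLQ count.

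Three stronger readings are tempting, and the documents do not support them.

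- A reader might infer that sections 7.5.1 and 7.5.3 contradict each other. Each rule is tied to its own calculation, the first to summary statistics and the second to noncompartmental PK parameters. Different conventions for the two are not in themselves an error.
- A reader might infer that the instruction "When calculating the GM, values of 0 will be discarded" is empty because no BLQ value is ever zero. In 7.5.2 the same statistics are applied to changes from Baseline, and a participant who is BLQ at both times has a change of exactly zero. The sentence has work to do there.
- A reader might infer that falls in toxic copper are hidden altogether. A fall down to the LLOQ still shows, and individual values are listed. Only the part below the LLOQ is lost, and only from the summaries and PD parameters.

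**Conclusion.** The point holds, at minor severity. The substitution can only raise low values, and from a quantifiable Baseline it caps the apparent fall in PUF Cu and LBC at LLOQ/Baseline - 1. Both follow from the rule without further assumption. How much this matters depends on the BLQ rate, which is unknown. Under a lognormal with CV 40%, the error in percent change is about 13 to 28 points at 82% to 99% BLQ, about 6 points at 50% and about 1 point at 15%. The serious distortion is therefore confined to time points where most values are BLQ, and the SAP plans nothing that would show the reader which those are.

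The primary Cu balance endpoint does not use these plasma rules. LBC enters one descriptive secondary endpoint and one exploratory endpoint, and PUF Cu is named in no objective or endpoint. No hypothesis test is involved.

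**What to change.** - **SAP 7.5.1 and 7.5.2:** add the number and percentage BLQ for each analyte and time point. Where more than half are BLQ, report the median as `<LLOQ`, which is then exactly true, and give no mean, SD, geometric mean or mean change from Baseline.
- **SAP 7.5.4:** flag each PD parameter that rests on a substituted value.
- **Leave as they are:** the LLOQ substitution at or below 50% BLQ, since LLOQ/2 is not clearly better there and overstates the fall in the cases checked; and the zero-value sentence in 7.5.2.

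The cost is a few lines of SAP text and minor programming. The downside is that some time points may carry no mean, so a mean profile could have gaps. If BLQ values turn out to be rare, the only visible change is a column of small counts.
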